## **9. PHARMACOKINETIC EVALUATION**

No pharmacokinetic sampling is planned for this study.

## 10. OTHER ANALYSES

Dose response and tolerability for dasotraline treated subjects will also be analyzed in a weight-based dose-level analysis. Dose per weight (mg/kg) will be calculated for each dasotraline treated subject and then placed into the following groupings:

- 2 equal-sized groups: 2 groups will be formed based on the median number of dasotraline treated subjects. Each group will contain half of the population of dasotraline treated subjects.
- 3 equal-sized groups: 3 groups will be formed based on tertiles of the number of dasotraline treated subjects. Each group will contain a third of the population of dasotraline treated subjects.

Each of these groupings will be analyzed using the same primary efficacy analysis method described in Section 7.5.1. In addition, each of these groupings will be analyzed for safety summarized by PT in descending order for each of the following categories: AEs, SAEs, AEs leading to discontinuation, and AEs of special concern.

A Receiver Operating Characteristic (ROC) analysis will also be conducted based on a logistic regression with dose per weight (mg/kg) as the predictor and AE of special concern as the outcome. An ROC curve for the model will be plotted. The predicted probability of having an AE of special concern event will also be plotted as a function of dose per weight (mg/kg).

Any additional analyses performed after finalization of the SAP will be considered exploratory and will be identified as such in the CSR.

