2. Subject has a diagnosis of bipolar I or II disorder, major depressive disorder, conduct disorder, obsessive-compulsive disorder, disruptive mood dysregulation disorder (DMDD), intellectual disability, any history of psychosis, autism spectrum disorder, Tourette's Syndrome, or confirmed genetic disorder with cognitive and/or behavioral disturbances; generalized anxiety disorder or panic disorder that has been the primary focus of treatment at any time during the 12 months prior to screening; or that required pharmacotherapy any time during the 6 months prior to the start of screening.
3. Subject has failed 2 adequate courses (dose and duration) of stimulant or non-stimulant treatment for ADHD.
4. Subject is considered treatment refractory by the investigator.
5. Subject shows evidence of any chronic disease of the central nervous system (CNS) such as tumors, inflammation, seizure disorder, vascular disorder, potential CNS related disorders that might occur in childhood.
6. Subjects with a history of persistent neurological symptoms attributable to serious head injury; history of febrile seizure, drug-induced seizure, or alcohol withdrawal seizure.
7. Any use of anticonvulsants for seizure control currently or within the past 2 years.
8. Uncontrolled thyroid disorder indicated by thyroid stimulating hormone (TSH) $\leq 0.8 \times$ the lower limit of normal (LLN) or $\geq 1.25 \times$ the upper limit of normal (ULN) for the reference laboratory.
9. Any history of attempted suicide, clinically significant suicidal ideation, or answers "yes" to "Suicidal Ideation" item 4 or item 5 for any lifetime history on the C-SSRS Children's Lifetime/Recent assessment at screening.
10. Subjects having first-degree relatives (biological parent or sibling) with a history of schizophrenia, schizoaffective disorder, bipolar I disorder, or bipolar II disorder are also ineligible for the study.

Investigational Product, Dosage and Mode of Administration: Each daily dose will be supplied as one 2 mg dasotraline capsule for oral administration.

Duration of Treatment: 2 weeks

Reference Therapy, Dosage and Mode of Administration: Each daily dose will be supplied as one matching placebo capsule for oral administration.

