## 2.5 Treatment Regimens

Under supervision from the subject's parent/legal guardian, subjects will self-administer the study drug on an outpatient basis for 14 days beginning the evening of Day 1. Study drug should be taken at approximately the same time each evening. The first dose of study drug may be administered in the clinic, after all assessments are completed, before the subject leaves, or at home. On Day 14, the night before the second classroom day, study drug must be taken at 8 PM plus or minus 30 minutes. All study medication doses will consist of 1 capsule per day taken by mouth.

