## 7.5 Analysis Methods

### 7.5.1 Primary Efficacy Analyses

The primary efficacy analysis will be performed on the ITT population. The primary efficacy outcome is the change from baseline (Visit 4) at Day 15 (Visit 5) in ADHD symptoms as measured by mean SKAMP-CS obtained from an average of the 7 assessments collected across the 12 hour classroom day (12 to 24 hours post-dose).

The key elements of the primary efficacy analysis are as follows:

**Data:** Change from baseline at Day 15 of mean SKAMP-CS measured on the laboratory classroom days, Visits 4 (baseline) and 5 (Day 15). Mean SKAMP-CS will be calculated by taking the average across all 7 assessment time points (8:00 am, 10:00 am, 12:00 pm, 2:00 pm, 4:00 pm, 6:00 pm, and 8:00 pm) both at baseline and at Day 15. The mean SKAMP-CS will not be rounded prior to analysis. Missing individual item data will first be imputed as described in Section 7.1.1.1 before taking the mean across all assessment time points.

**Model:** ANCOVA

**Fixed effects:** The following fixed effects are planned:

- Treatment
- Mean SKAMP-CS at baseline (Visit 4)
- Site (or pooled site if some sites to be pooled)

The null hypothesis:

$H_0$ : Change from baseline at Day 15 of the mean SKAMP-CS over all time points from 8:00 am to 8:00 pm on the laboratory classroom days are the same for dasotraline 2 mg/day and placebo

will be tested against the 2-sided alternative hypothesis:

H1: Change from baseline at Day 15 of the mean SKAMP-CS over all time points from 8:00 am to 8:00 pm on the laboratory classroom days are not the same for dasotraline 2 mg/day and placebo.

The average treatment difference over all post-dose time points will be estimated using LS means from the ANCOVA. The treatment comparison will be conducted as a 2-sided test at the 5% level of significance. The standard error and 95% confidence interval for the treatment difference as well as the treatment effect size will be provided. Effect size will be calculated as the absolute value of the LS mean treatment difference divided by the observed pooled standard deviation, which will be calculated using the following formula:

$$SD = SE(\bar{x}_d) / \sqrt{1/N_{PBO} + 1/N_{DAS}}, \text{ where } \bar{x}_d \text{ is the LS mean treatment difference.}$$

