### **7.5.3 Examination of Subgroups**

The primary efficacy analyses will be repeated on the ITT population based on the following subgroups:

- Sex (Male and Female)
- Race (White, Black or African American, and Other)
- Age (6-9 years and 10-12 years)
- Previous treatment (stimulant and treatment-naïve)

The interaction of each subgroup with the treatment effect will also be measured. The primary efficacy analysis will be repeated on the ITT population once for each subgroup above, with the subgroup of interest added as a fixed effect, along with the interaction between the subgroup of interest and the treatment effect. The p-values from the resulting tests for interaction will be summarized.

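### The SAP Section 10 mg/kg 'dose response' groups are body-weight groups formed in the dasotraline arm only, with no weight-grouped placebo comparator and no treatment-by-weight interaction

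*SAP*

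**What the plan says.** SAP Section 10 introduces the analysis with "Dose response and tolerability for dasotraline treated subjects will also be analyzed in a weight-based dose-level analysis". It then defines the groups: "Dose per weight (mg/kg) will be calculated for each dasotraline treated subject and then placed into the following groupings". These are two groups split at the median and three split at the tertiles of the dasotraline-treated children. For efficacy, "Each of these groupings will be analyzed using the same primary efficacy analysis method described in Section 7.5.1".

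SAP 7.5.1 is a two-arm comparison. Its null hypothesis is that mean SKAMP-CS changes "on the laboratory classroom days are the same for dasotraline 2 mg/day and placebo", and its fixed effects are treatment, baseline mean SKAMP-CS and site.

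The dose is the same for every active child. The Protocol synopsis says "Each daily dose will be supplied as one 2 mg dasotraline capsule for oral administration", and SAP 2.5 says "All study medication doses will consist of 1 capsule per day taken by mouth".

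In SAP 7.5.3, "The interaction of each subgroup with the treatment effect will also be measured", but the subgroups listed are sex, race, age (6-9 and 10-12 years) and previous treatment. SAP 7.5.2 calls the mg/kg efficacy analysis secondary and refers to Section 10 for details. Protocol 15.3.5.2 promises weight-based efficacy analyses without giving a method.

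**The concern.** With one fixed dose there is no randomised dose contrast inside the active arm. Ranking children by mg/kg is ranking them by weight in reverse. Each group is thus a set of dasotraline children selected on weight, while the placebo children are never grouped by weight. If lighter and heavier children differ in SKAMP change for reasons unrelated to the drug, that difference is added to one group's apparent effect and taken from the other's.

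The result is likely to be read as pharmacology. Section 10 uses the words dose response. The sample-size rationale (Protocol 15.1, SAP 2.6) rests partly on an effect of 0.70 seen in a range of mg/kg doses, and the population rationale (Protocol 7.3.2 and 7.3.3) is also argued in mg/kg. At stake is the interpretation of this secondary analysis. No decision rule depends on it.

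**Working it through.** **Plan's own figure.** SAP 2.6 gives 44 per arm for an effect of 0.7 SD, two-sided 0.05, 90% power by t-test. Noncentral-t power is 0.901 at 44 per arm and 0.894 at 43, so the figure reproduces. 100 randomised x 0.88 = 88 completers. The SAP gives no figure for the Section 10 analysis.

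**mg/kg is weight.** 2/16 = 0.125 mg/kg and 2/30 = 0.067 mg/kg, and the relation is exact and decreasing. (The plan's lower limit of 0.057 mg/kg corresponds to 2/0.057 = 35 kg, above the 30 kg entry limit; those passages need reconciling.)

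**Inputs for the comparison.** From the plan: 44 per arm, hence 22 active children per half, and a true effect of 0.70 SD taken as the same at every weight. Assumed: weight roughly normal; r is the correlation of weight with SKAMP change after baseline and site adjustment, positive when heavier children improve less. No document gives r, so 0 to 0.3 is shown.

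**Each group against all placebo.** The mean standardised weight is -0.798 and +0.798 in the two halves, and -1.091 and +1.091 in the outer tertiles. Apparent effect = 0.70 +/- 0.798r (halves) or 0.70 +/- 1.091r (outer tertiles).

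| r | Light v heavy half | Light v heavy tertile |
|---|---|---|
| 0 | 0.70 v 0.70 | 0.70 v 0.70 |
| 0.1 | 0.78 v 0.62 | 0.81 v 0.59 |
| 0.2 | 0.86 v 0.54 | 0.92 v 0.48 |
| 0.3 | 0.94 v 0.46 | 1.03 v 0.37 |

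A negative r reverses the order. Simulation with the ANCOVA (baseline, 5 sites, 2,000 trials per setting) gave 0.78 v 0.62, 0.86 v 0.55 and 0.93 v 0.48 for halves at r = 0.1, 0.2 and 0.3. Against a 95% half-width of 0.54 SD for one half, the shift of 0.08, 0.16 or 0.24 SD is 15%, 30% or 44%.

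**Same cut-points in both arms.** The simulated effect was 0.69-0.72 in both bands at every r, so the artefact disappears. The half-width rises to about 0.65 SD.

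**One model with continuous weight.** Normal-approximation variances for the light-half effect, in SD squared:
- all placebo: 1/22 + 1/44 = 0.0682, plus squared bias (0.798r)^2 = 0.637r^2;
- matched bands: 2/22 = 0.0909;
- treatment, weight and treatment-by-weight: (2/44)(1 + 0.798^2) = 0.0744, unbiased if the relation is linear.

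On mean squared error, matched bands beat the all-placebo comparison only when |r| exceeds sqrt((0.0909 - 0.0682)/0.637) = 0.19. The continuous model does so once |r| exceeds sqrt((0.0744 - 0.0682)/0.637) = 0.10. In simulation over r = 0 to 0.3, the continuous model's light-half effect stayed at about 0.70 with root mean squared error about 0.28. The all-placebo comparison ran from 0.27 to 0.37, and matched bands were about 0.32.

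**Interaction precision.** The SE is sqrt(2/44) = 0.213 SD per SD of weight, so 80% power needs 2.80 x 0.213 = 0.60. With halves the SE is sqrt(4/22) = 0.426, and 80% power needs a difference of 1.19 SD.

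**The case against.** The best reply is that Section 10 never says the groups are compared with the whole placebo arm. It is silent, and SAP Section 1 places table specifications in documents not available here. That stands: a reader might infer that an unmatched comparison is specified, and the text does not support it. The supportable statement is that the comparator is undefined and nothing in the plan groups placebo by weight. If the comparison were instead among dasotraline groups only, dose and weight would be fully confounded.

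A reader might also infer that the weight used for mg/kg is undefined, since weight is measured at four visits. SAP 7.1.3 defines baseline for vital signs as the last value before first dose, and SAP 8.8 counts body weight among vital signs. That largely settles it; only a cross-reference is missing.

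The size depends wholly on r, for which the documents offer no evidence, and the shift is small at r = 0.1. That also stands. So does the point that matched bands alone lose accuracy when r is small, which is why the continuous model is preferable. Baseline SKAMP adjustment and the age interaction cover weight only in part.

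Two further inferences go too far. Section 10 plans no between-group or trend test, so no false-positive rate of a planned test is at issue. The logistic regression and ROC curve for adverse events of special concern in Section 10 ("A Receiver Operating Characteristic (ROC) analysis will also be conducted based on a logistic regression with dose per weight (mg/kg) as the predictor") can serve as prediction among treated children; the same caution about calling it a dose relation applies, but the efficacy bias shown here does not make it invalid.

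**Conclusion.** The point holds for the interpretation of a secondary analysis. As written, Section 10 compares weight-selected dasotraline children with placebo children who have no weight grouping, through a model with no weight term, and the plan contains no treatment-by-weight interaction. If all placebo is the comparator, the spurious difference between halves is 2 x 0.798r, or 0.16, 0.32 and 0.48 SD at r = 0.1, 0.2 and 0.3, under a constant 0.70 SD effect with 44 per arm. It is zero at r = 0. The r range and the all-placebo reading are assumptions. The primary analysis, its significance level and the sample size are unaffected. This is worth changing because the remedy is cheap, not because the trial's conclusion depends on it.

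**What to change.** - Make the main Section 10 efficacy analysis one ITT model with treatment, continuous baseline weight (pre-dose, citing SAP 7.1.3), treatment-by-weight, baseline mean SKAMP-CS and site pooled as in SAP 7.1.2. Report the interaction estimate with its 95% CI.
- Add weight to the SAP 7.5.3 interaction list.
- If halves and tertiles are kept, apply the same weight cut-points to both arms and report dasotraline versus placebo within each band as descriptive.
- Describe the result as effect modification by weight, and state that one fixed dose cannot separate this from age or from an mg/kg dose effect.

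The cost is SAP text and some programming, since weight is already collected in both arms. Intervals within bands widen: for halves the half-width goes from about 0.54 to 0.65 SD with 5 sites, and slightly more with the 7 levels that SAP 7.1.2 allows (up to 8 sites, two pooled into one). For tertiles it goes from about 0.62 to 0.85 SD. Interaction power is low (0.60 SD per SD of weight for 80%), so the SAP should say that a null interaction is not evidence of no gradient.

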## **11. INTERIM ANALYSES AND DATA MONITORING**

No interim analyses are planned for this study. The Data and Safety Monitoring Board (DSMB) will monitor safety throughout the study. The DSMB will be independent of the Sponsor, CRO, and the investigators and will be empowered to recommend stopping the study due to safety concerns. The membership of the DSMB and its mandate will be described in a separate DSMB charter.

## **12. CHANGES TO STUDY CONDUCT OR ANALYSES PLANNED IN THE PROTOCOL**

### **12.1 Changes in the Conduct of the Study**

The protocol underwent 3 amendments over the course of the study.

- Protocol Version 2.00 Amendment 1.00, finalized 29 June 2017
- Protocol Version 3.00 Amendment 2.00, finalized 19 November 2017
- Protocol Version 4.00 Amendment 3.00, finalized 22 June 2018

Refer to the individual protocol versions for details on each amendment.

### **12.2 Changes in the Analysis Planned in the Protocol**

No changes are planned as of the date of the SAP.

## 14. APPENDICES

### 14.1 Schedule of Events

Procedures	Screening			Double-blind Period		End of Study
	Clinic Visit	Practice Laboratory Classroom Session	Telephone Contact	First Laboratory Classroom Day	Second Laboratory Classroom Day	-
	Visit 1	Visit 2	Visit 3	Visit 4	Visit 5	Visit 6
	Day -42 to -8	Day -7	Day -1	Day 1	Day 15	Day 21 a (± 2)
Obtain informed consent	X					
Obtain informed assent	X					
Inclusion/Exclusion criteria	X	X	X	X		
Randomization				X		
Dispense study drug				X		
Study drug accountability					X	
Medical History	X					
Psychiatric History	X					
Family Psychiatric History	X					
Prior/concomitant medication review	X	X	X	X	X	X
K-SADS-PL	X					
Physical examination	X					X
Neurological examination	X					X
Height	X					
Weight (including body mass index)	X			X	X	X
Vital signs	X	X		X b	X b	X
Electrocardiogram (ECG)	X					X
Adverse event monitoring f					X	X

Procedures	Screening			Double-blind Period		End of Study
	Clinic Visit	Practice Laboratory Classroom Session	Telephone Contact	First Laboratory Classroom Day	Second Laboratory Classroom Day	-
	Visit 1	Visit 2	Visit 3	Visit 4	Visit 5	Visit 6
	Day -42 to -8	Day -7	Day -1	Day 1	Day 15	Day 21 a (± 2)
Columbia Suicide Severity Rating Scale (C-SSRS)	X	X		X	X	X
ADHD-RS-IV HV	X	X g	X			X
Classroom Practice Session c		X				
SKAMP d				X	X	
Math pre-test for determination of math level	X					
PERMP d				X	X	
Dosing diary distribution/review				X	X	
Hematology/Chemistry	X					X
TSH	X					
Serum β-hCG (in females ≥ 8 years of age) e	X					X
Urinalysis	X					X
Urine drug screen	X			X	X	X
Urine β-hCG (in females ≥ 8 years of age) e				X	X	

Abbreviations: ADHD-RS-IV HV = ADHD Rating Scale Version IV Home Version (modified for investigator administration), β-hCG = beta-human chorionic gonadotropin, K-SADS-PL = Schedule for Affective Disorders and Schizophrenia for School-Age Children- Present and Lifetime version, PERMP = Permanent Product Measure of Performance, SKAMP = Swanson, Kotkin, Agler, M-Flynn, and Pelham Scale, TSH = thyroid stimulating hormone

a Seven (± 2) days after the last dose of study drug, all subjects will return to the clinic and complete assessments.

b Heart rate and blood pressure will be measured at approximately the same time on Day 1 and Day 15.

c Including practice SKAMP assessments, practice PERMP tests, and other planned activities intended to familiarize subjects with the classroom setting.

d Classroom sessions will be started at approximately 8 AM, 10 AM, 12 PM, 2 PM, 4 PM, 6 PM, and 8 PM.

e Any positive urine β-hCG test should be confirmed by serum β-hCG.

f Pre-treatment events will be collected from the time of informed consent until the first study drug administration.

g The ADHD-RS-IV HV may be completed in person or by telephone contact on Day -9, -8, or -7.

### 14.2 Sample Laboratory Classroom Day Schedule (Day 15)

Nominal Time	Actual Time	Arrival	PERMP/SKAMP	Meal/snack	Dismissal
	6:30 am	X			
	7:30 am			X	
12 h post-dose	8:00 am		X		
	9:45 am			X	
14 h post-dose	10:00 am		X		
16 h post-dose	12:00 pm		X		
	12:30 pm			X	
18 h post-dose	2:00 pm		X		
	2:30 pm			X	
20 h post-dose	4:00 pm		X		
22 h post-dose	6:00 pm		X		
	6:30 pm			X	
24 h post-dose	8:00 pm		X		
	8:45 pm				X

### 14.3 SKAMP Rating Scale and Subscales

Subscale	Item
Attention	1. Getting started on assignments for classroom periods
	2. Sticking with tasks or activities for the allotted time
	3. Attending to an activity or a discussion of the class
	4. Stopping and making transition to the next period
Department	5. Interacting with other children (e.g., other students)
	6. Interacting with adults (e.g., teacher or aide)
	7. Remaining quiet according to classroom rules
	8. Staying seated according to classroom rules
Quality of Work	9. Completing assigned work
	10. Performing work accurately
	11. Being careful and neat while writing or drawing
Compliance	12. Complying with teacher's usual requests or directions
	13. Following the rules established for the classroom

### 14.4 Laboratory Criteria for Markedly Abnormal Values

Parameter (Unit)	Markedly Abnormal Range (Conventional Unit)	Conversion Factor (Conventional to SI) / SI unit	SI Unit Markedly Abnormal Range
Hematology			
Hemoglobin (g/dL)	Female: $\leq 9.5$ , Male: $\leq 11.5$ $\geq 17.2$	10 / g/L	Female: $\leq 95$ g/L, Male: $\leq 115$ g/L, $\geq 172$ g/L
Haematocrit (fraction, %)	$\leq 30$ , $\geq 50$	1 / %	$\leq 30$ , $\geq 50$ (1)
WBC ( $10^3/\mu\text{L}$ )	$\leq 2.8$ , $\geq 16$	1 / $\times 10^9/\text{L}$ (PPD Conv unit K/cu mm)	$\leq 2.8$ , $\geq 16$
RBC ( $10^6/\mu\text{L}$ )	$\leq 3.0$ , $\geq 6.0$	1 / $\times 10^{12}/\text{L}$ (PPD Conv unit $\times 10^6/\text{cu mm}$ )	$\leq 3.0$ , $\geq 6.0$
Platelet Count ( $10^3/\mu\text{L}$ )	$\leq 100$ , $\geq 500$	1 / $\times 10^9/\text{L}$ (PPD Conv unit K/cu mm)	$\leq 100$ , $\geq 500$
Eosinophils (%)	$\geq 10$	1 / %	$\geq 10$
Neutrophils (%)	$\leq 15$	1 / %	$\leq 15$
Clinical Chemistry			
ALP (U/L)	$\geq 3 \times \text{ULN}$	1 / U/L	$\geq 3 \times \text{ULN}$
ALT (U/L)	$\geq 2 \times \text{ULN}$	1 / U/L	$\geq 2 \times \text{ULN}$
AST (U/L)	$\geq 2 \times \text{ULN}$	1 / U/L	$\geq 2 \times \text{ULN}$
Total Bilirubin (mg/dL)	$\geq 2.0$	17.1 / $\mu\text{mol/L}$	$\geq 34.2$
Albumin (g/dL)	$< 50\% \text{ LLN}$	10 / g/L	$< 50\% \text{ LLN}$
Creatinine (mg/dL)	$\geq 2.0$	88.4 / $\mu\text{mol/L}$	$\geq 176$
Creatine Phosphokinase (CPK) (U/L)	$\geq 450$	1 / U/L	$\geq 450$
LDH (U/L)	$\geq 3 \times \text{ULN}$	1 / U/L	$\geq 3 \times \text{ULN}$
GGT (U/L)	$\geq 150$	1 / U/L	$\geq 150$
Sodium (mEq/L)	$\leq 130$ , $\geq 150$	1 / mmol/L	$\leq 130$ , $\geq 150$
Potassium (mEq/L)	$\leq 3$ , $\geq 5.5$	1 / mmol/L	$\leq 3$ , $\geq 5.5$
Bicarbonate (mEq/L)	$< 18$ , $> 30$	1 / mmol/L	$< 18$ , $> 30$
Calcium (mg/dL)	$< 8.4$ , or $> 11.5$	0.25 / mmol/L	$< 2.1$ , or $> 2.8$
Chloride (mEq/L)	$< 90$ , $> 115$	1 / mmol/L	$< 90$ , $> 115$
Blood Urea Nitrogen (mg/dL)	$\geq 30$	0.357 / mmol/L	$> 10.7$
Glucose (fasting) (mg/dL)	$\leq 45$ , $\geq 126$	0.05551 / mmol/L	$\leq 2.5$ , $\geq 11.1$
Glucose (random) (mg/dL)	$\leq 45$ , $> 200$	0.05551 / mmol/L	$\leq 2.5$ , $\geq 11.1$
Urinalysis			
RBC (hpf)	$> 15$	N/A	$> 15$
WBC (hpf)	$> 15$	N/A	$> 15$

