### **8.6 Clinical Laboratory Evaluations**

The following laboratory tests will be performed at Screening (Visit 1) and EOS (Visit 6):

- Clinical Chemistry: Alanine aminotransferase (ALT), Alkaline Phosphatase (ALP), Aspartate aminotransferase (AST), Bicarbonate (HCO3), Bilirubin (Total, Direct, Indirect), Blood Urea Nitrogen (BUN), Calcium (Ca), Chloride (Cl), Creatinine, Glucose, Magnesium (Mg), Phosphorus (P), Potassium (K), Protein (Total), Sodium (Na), Uric Acid, Albumin
- Hematology: Hemoglobin, Hematocrit, Platelet Count, RBC Count, WBC - Total Count, WBC Differential, (Basophils, Eosinophils, Lymphocytes, Monocytes, Neutrophils)
- Urinalysis: Blood, Glucose, Ketones, Leukocyte esterase, Microscopic examination, Nitrites, pH, Protein

Summary statistics for these laboratory panels (clinical chemistry, hematology and urinalysis) will be provided by treatment group and visit. Laboratory data will also be summarized in shift tables presenting summary statistics of raw data and change from baseline values (means, standard deviations, medians, ranges). All clinical laboratory assessments will be listed for each panel.

In addition, the incidence of markedly abnormal post-baseline laboratory values (MAPLV) will be presented to examine the frequency and percentage of subjects that have values that are potentially clinically significant (PCS). These abnormal values will also be flagged in the laboratory listings. These criteria are outlined in Appendix 14.4.

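### SAP Appendix 14.4: the two unit columns for fasting glucose disagree (126 mg/dL converts to 7.0 mmol/L, not 11.1), so a markedly-abnormal flag on a fasting sample can depend on the unit programmed

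*SAP*

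**What the plan says.** SAP Section 8.6 states that "the incidence of markedly abnormal post-baseline laboratory values (MAPLV) will be presented", and adds: "These abnormal values will also be flagged in the laboratory listings". It then gives the source: "These criteria are outlined in Appendix 14.4". Appendix 14.4 is therefore the operative rule for one summary table and one set of listing flags.

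For each parameter the appendix gives a conventional-unit limit, a factor for converting conventional to SI units, and an SI limit. There are two glucose rows:

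- "Glucose (fasting) (mg/dL": ≤45 or ≥126 mg/dL; SI limits ≤2.5 or ≥11.1 mmol/L.
- "Glucose (random) (mg/dL": ≤45 or >200 mg/dL; SI limits ≤2.5 or ≥11.1 mmol/L.

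Both rows carry the same factor, "0.05551 / mmol/L". Their conventional upper limits differ, but their SI cells are identical.

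The calcium row gives <8.4 or >11.5 mg/dL, factor 0.25, and SI limits <2.1 or >2.8 mmol/L.

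Neither Section 8.6 nor the appendix says which unit column is to be applied.

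**The concern.** The SI column is meant to restate the conventional column in other units. In the fasting-glucose row it does not: the two upper limits describe different glucose concentrations. Since the SAP does not say which column is used, the pre-specified criterion for a fasting sample is ambiguous. A fasting value of 150 mg/dL (150 × 0.05551 = 8.3 mmol/L) is markedly abnormal by one column and not by the other.

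What is at stake is the count of potentially clinically significant glucose values by arm, and the flag in the by-subject listing. Laboratory tests are scheduled only at Visit 1 and Visit 6, so each child has one scheduled post-baseline glucose. With about 50 children per arm, one reclassified child moves that arm's incidence by 1/50, or 2 percentage points.

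**Working it through.** **Inputs.** All limits and factors are from SAP Appendix 14.4. The formula is SI limit = conventional limit × stated factor.

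**Limits that reproduce.** These show that the factor and the columns have been read correctly.

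- Glucose lower limit, both rows: 45 × 0.05551 = 2.498, stated as 2.5.
- Random glucose upper limit: 200 × 0.05551 = 11.102, stated as 11.1.

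**The limit that does not reproduce.**

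- Fasting glucose upper limit: 126 × 0.05551 = 6.994, or 7.0 mmol/L; stated as 11.1.
- Ratio: 11.1 / 6.994 = 1.587, so the stated SI limit is about 59% too high.
- Converted back: 11.1 / 0.05551 = 199.96 mg/dL, which is the random-glucose limit.

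**Other rows with a factor other than 1 and a numeric limit.**

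| Limit | Conventional × factor | Stated SI | Difference |
|---|---|---|---|
| Hemoglobin (three limits) | 9.5, 11.5, 17.2 × 10 = 95, 115, 172 | 95, 115, 172 | none |
| Total bilirubin | 2.0 × 17.1 = 34.2 | 34.2 | none |
| Creatinine | 2.0 × 88.4 = 176.8 | 176 | −0.5% |
| Blood urea nitrogen | 30 × 0.357 = 10.71 | 10.7 | −0.1% |
| Calcium, low | 8.4 × 0.25 = 2.1 | 2.1 | none |
| Calcium, high | 11.5 × 0.25 = 2.875 | 2.8 | −2.6% |

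Fasting glucose is the only gross mismatch. Calcium is a smaller one: 2.8 / 0.25 = 11.2 mg/dL, so the SI column would flag values above 11.2 and up to 11.5 mg/dL that the conventional column does not.

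**Effect on a fasting sample.**

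| Value | Conventional column | SI column |
|---|---|---|
| below 126 mg/dL (above 45) | not flagged | not flagged |
| 126 to just below 200 mg/dL (7.0 to below 11.1 mmol/L) | flagged | not flagged |
| 11.1 mmol/L or more | flagged | flagged |

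**Inequality signs.** Two rows change sign between columns.

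- Blood urea nitrogen is ≥30 mg/dL but >10.7 mmol/L. A value of 30 gives 10.71, flagged in both columns; 29 × 0.357 = 10.35, flagged in neither. Whole-number mg/dL results are classified alike.
- Random glucose is >200 mg/dL but ≥11.1 mmol/L. The columns differ essentially only at 200 mg/dL itself (11.102 mmol/L).

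**The case against.** The best case on the other side accepts the arithmetic and disputes the consequence.

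1. *The loss of flags is conditional.* A reader might infer that abnormal fasting values will go unflagged. The documents do not support that. It requires the SI column to be programmed and the sample to be classed as fasting, and neither is established. Under the conventional column every fasting value of 126 mg/dL or more is flagged, and even under SI those at 11.1 mmol/L or more still are. This limit stands.

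2. *The fasting row may never operate.* Protocol Appendix III and SAP Section 8.6 list glucose without qualification. Neither the visit descriptions nor the laboratory section of the protocol requires fasting, and nothing says that fasting status is recorded. Appendix 14.4 also has rows for CPK, LDH and GGT, which are in neither panel, so the table is wider than this trial's tests. This stands too. However, if fasting status is unknown, the programmer must still choose between two rows whose conventional limits differ, and the SAP gives no rule.

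3. *Clinical detection does not run through this table.* A reader might infer that an affected child would be overlooked. Under Protocol Section 12.2, values outside the normal range are brought to the investigator's attention, the investigator judges significance, and significant post-dose abnormalities are recorded as adverse events. None of this uses Appendix 14.4, and SAP Section 8.6 lists all laboratory results in any case. The exposure is confined to a descriptive display.

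4. *Most of the remaining differences are trivial.* It would be wrong to say that every change of sign alters a classification: the blood urea nitrogen one does not for whole-number values, and the random-glucose one is tidy-up. Calcium looks like truncation to one decimal, as with creatinine, though it does move the limit by 0.3 mg/dL.

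The identical SI cells suggest that one was carried over from the other row, but that is inference. The mismatch does not depend on how it arose.

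**Conclusion.** The point holds as an internal inconsistency. By the table's own factor, the fasting-glucose limit of 126 mg/dL is 7.0 mmol/L, and the stated 11.1 mmol/L is 200 mg/dL. Nothing elsewhere in the SAP corrects it.

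Its practical size is the number of post-baseline samples that are classed as fasting, lie between 126 and about 200 mg/dL, and are judged by the SI column. The documents do not allow that number to be estimated; it may be small or zero. The calcium upper limit is a second, lesser mismatch.

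This is a minor correction to a descriptive safety table and its listing flags. It does not touch the primary efficacy analysis, and it does not show that any abnormal result would escape investigator review.

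**What to change.** Either of two changes to Appendix 14.4 would settle it:

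- Make the SI limits follow from the conventional limits and the stated factors: fasting glucose ≥7.0 mmol/L and calcium >2.875 mmol/L.
- Apply the criteria in conventional units only, and say so in Section 8.6.

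If the SI limits are kept, state how results are rounded before comparison. SAP Section 3 rules out rounding before analysis, and 126 mg/dL converts to 6.994, which would just miss a limit of 7.0 on unrounded values. Applying the limits in conventional units avoids this.

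In either case, name the unit column that governs the incidence table and flags, and state which glucose row applies when fasting status is not recorded. Aligning the inequality signs between columns can be done at the same time as tidy-up.

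The cost is a table edit and a sentence or two in the SAP, with no change to data collection. If the displays are already programmed, which the documents do not say, the glucose and calcium flags would need to be rechecked. Section 7.1.2 describes a site's enrolment in the past tense, so this is a late-stage plan.
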